## **STUDY TYPE**

An observational study of paired cohorts, not randomized, is designed in two hospitals in northern Spain in the period between october 2023 and september 2024.

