## PROTOCOL

All patients will be trained preoperatively in pain assessment using a Numerical Rating Scale (NRS) from 0 (absence of pain) to 10 (maximum pain endured). All patients will receive the same anesthesia and analgesia protocol; fentanyl, propofol and rocuronium prior to intubation.

Anesthetic maintenance with 1 MAC of sevoflurane and boluses of muscle relaxant and fentanyl if there is an increase >20% in blood pressure or above baseline heart rate. The anesthetic protocol will include analgesia with 1 g of paracetamol and 50 mg of dexketoprofen every 8 hours and a bolus of 0.1 mg/kg of intravenous dexamethasone. When the patient reports an NRS > 3 and functional impact, intravenous morphine will be administered at a dose of 0.04 mg/kg every 10 minutes until NRS < 3 in the PACU and tramadol 1 mg/kg in the ward. The nursing staff and the anesthesiologist in charge of the PACU will be blind to the block received by the patient in each study group.

Before general anesthesia, patients will be assigned to one of the study groups depending on the anesthesiologist responsible for performing the blocks.

**SHAC + SSN Group (anterior approach):** with the patient in the supine position and the arm placed in abduction and slight external rotation the ultrasound probe will be positioned in the transverse axis between the coracoid process and the humeral head. After identifying the tendon of the subscapularis muscle, a puncture will be performed in a lateral to medial plane and the local anesthetic will be deposited at two levels; one deep to the subscapularis tendon at the pericapsular level of the glenohumeral joint (5 ml of ropivacaine 0.2%), and another in withdrawal at about the level of the fascia that separates the subscapularis and deltoid muscles at a more superficial level (10 ml of 0.2% ropivacaine). Subsequently, the ultrasound probe will be positioned in the transverse axis at level with the neck to locate the suprascapular nerve through an anterior approach as it ran beneath the omohyoid muscle. After hydrodissecting the correct plane with saline solution 5 ml of 0.2% ropivacaine will be administered, depositing the local anesthetic under the lower belly of the omohyoid muscle.

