## **RECRUITMENT AND RECRUITMENT OF PARTICIPANTS**

The anesthesiologist responsible for the operating room performed both the block of the anterior capsule of the shoulder and the suprascapular nerve via the anterior route and the blocks of the suprascapular and axillary nerves via the posterior route until the number of patients established in each of the groups is reached.

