## **JUSTIFICATION OF SAMPLE SIZE**

Because no work of this nature has been carried out previously, a sample size calculation will be not performed and all patients who underwent surgery in the 12 months that the study data collection will last were consecutively included in the study.

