## **VARIABLES EVALUATED**

The main variable will be the measurement of pain intensity according to the NRS at different times: preoperative and at the 1st, 2nd, 12th and 24th postoperative hours. As secondary variables, postoperative opioid requirements will be assessed in the form of intravenous morphine, measured in mg (only during the 2 hours of the patient's stay in the Postanesthesia Care Unit), and tramadol (mg) up to 24 hours postoperatively.

The degree of sensory block will be also assessed by a cold sensitivity test with a cotton swab dipped in cold water applied to the skin of the upper third of the arm, which will be graded with a sensitive scale going from 0 to 2 (2 being normal sensitivity to cold, 1 hypoesthesia and 0 anesthesia). The degree of motor block upon arrival at the PACU will be assessed by the movement of the arm using a simple numerical scale (0 = cannot raise the extended arm  $> 45^\circ$  and 1 = can raise the extended arm  $> 45^\circ$ ), the ease of performance of the corresponding anesthetic technique by the anesthesiologist using a simple verbal scale (easy/medium difficulty/difficult), the appearance of adverse effects (postoperative nausea and/or vomiting, hematoma, pruritus, urinary retention), the degree of patient satisfaction (very satisfied, satisfied or dissatisfied) and the notification of complications related to the anesthetic techniques performed.

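### The protocol conflicts on who delivers which block, and the plan neither records the operator nor allows for operator in the analysis, so operator differences could be credited to the technique

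*Combined protocol and SAP*

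**What the plan says.** All references are to the combined protocol and SAP.

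- **PROTOCOL.** This section gives the only sentence on how a patient reaches a group: "Before general anesthesia, patients will be assigned to one of the study groups depending on the anesthesiologist responsible for performing the blocks". It also blinds the PACU nursing staff and the PACU anesthesiologist to the block.
- **RECRUITMENT AND RECRUITMENT OF PARTICIPANTS.** This section begins: "The anesthesiologist responsible for the operating room performed both the block of the anterior capsule of the shoulder and the suprascapular nerve". The same sentence goes on to add the posterior technique. Here the same anesthesiologist gives both techniques and a target number per group governs. No such number is set anywhere: under JUSTIFICATION OF SAMPLE SIZE, "a sample size calculation will be not performed".
- **STUDY TYPE.** "An observational study of paired cohorts, not randomized, is designed in two hospitals in northern Spain". The basis of the pairing, the number of operators and their spread over the two hospitals are not given.
- **VARIABLES EVALUATED.** Operator identity and experience are not listed. One secondary variable is scored by the operator: "the ease of performance of the corresponding anesthetic technique by the anesthesiologist using a simple verbal scale (easy/medium difficulty/difficult".
- **STATISTICAL ANALYSIS PLAN.** Group comparisons use Student's t, Mann-Whitney, chi-square or Fisher tests, with Kruskal-Wallis and Bonferroni also mentioned. There is no operator or hospital term, no stratification and no regression model.

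**The concern.** In a non-randomised study, the rule that puts patients into groups decides what the group difference means. Here there are two rules. In one the operator determines the block; in the other the same operator gives both. Two hospitals could each follow a different section and both claim compliance.

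The choice matters because block quality depends on the person doing it. The background section describes SHAC as recently introduced, with only anatomical work and small case series published, so unequal skill and experience between those who use it and those who do not is plausible. If the groups are also groups of operators, a difference in pain, opioid use or block grade may belong to the operators. Ease of performance is the most exposed outcome: if each anesthesiologist uses one technique, each rating comes from someone who never rates the other.

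**Working it through.** The document states no sample size, power or effect size, so there is no figure of its own to reproduce. The check has three parts.

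**1. Can technique be separated from operator?** Take a model with an intercept, a technique term and one indicator per operator after the first.

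- *Each operator gives one block.* The technique column equals the sum of the indicators of the operators in that arm. The design matrix is therefore one short of full rank: 2 of 3 columns with one operator per arm, 4 of 5 with two, 8 of 9 with four. Technique is fully aliased with operator fixed effects.
- *Each operator gives both blocks.* The rank is full with the same numbers of operators (3 of 3, 5 of 5, 9 of 9). Technique can be estimated within operator, but only if operator is recorded and put in the model.

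**2. Does giving both blocks protect the planned unadjusted test?** Not by itself. Let operator j have effect u_j and supply share p1_j of one group and p0_j of the other. The unadjusted difference then contains Σ(p1_j − p0_j)·u_j. This vanishes for all u_j only if every operator supplies the same share of both groups. One block per operator is the extreme case; uneven use of both blocks is a milder one.

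**3. How large could the distortion be if operators are nested in arms?** All of the following are assumptions except the 5% level, which is in the analysis plan (two-sided is assumed, as the sidedness is not stated): NRS SD 2 within operator, n = 50 patients per arm, between-operator SD (SD_op) 0.3 or 0.5 points, k = 1, 2 or 4 operators per arm, no true technique effect, one test at one time point.

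- Nominal SE = 2·√(2/50) = 0.40.
- Operator variance of the arm difference = 2·SD_op²/k.
- True SE = √(0.40² + 2·SD_op²/k).
- Rejection rate = 2·(1 − Φ(1.96·0.40/true SE)), taking the test's own SE as 0.40.

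| k | SD_op 0.3: true SE | rejection | SD_op 0.5: true SE | rejection |
|---|---|---|---|---|
| 1 | √(0.16+0.18) = 0.583 | 17.9% | √(0.16+0.50) = 0.812 | 33.5% |
| 2 | √(0.16+0.09) = 0.500 | 11.7% | √(0.16+0.25) = 0.640 | 22.1% |
| 4 | √(0.16+0.045) = 0.453 | 8.3% | √(0.16+0.125) = 0.534 | 14.2% |

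These SDs correspond to intraclass correlations (ICC) of 0.09/4.09 = 0.02 and 0.25/4.25 = 0.06. The operator term does not contain n, so more patients per operator do not shrink it.

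A second route uses the design effect DE = 1 + (m − 1)·ICC, with m patients per operator and rejection rate 2·(1 − Φ(1.96/√DE)). With 40 patients per arm and ICC 0.01, 0.05 and 0.10:

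- one operator per arm: 10%, 25%, 38%
- two per arm: 7%, 16%, 25%
- four per arm: 6%, 10%, 16%

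Over 20 to 60 patients per arm the full range is 5.5% to 46%.

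These rates treat operators as random draws with the same expected skill in both arms. A systematic difference is worse. In a simulation of operator-level t-tests (5,000 runs per setting, 40 patients per arm, ICC 0.05, 2 or 4 operators per arm), the false-positive rate was 4.9% and 4.8% when the two sets of operators were exchangeable. When they differed by 0.3 or 0.5 SD, the mean technique estimate was 0.29 to 0.30 and 0.50 SD, so the whole difference passed into the estimate. At an SD of 2 that is 0.3·2 = 0.6 and 0.5·2 = 1.0 NRS points.

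**The case against.** The strongest reply is that the assignment sentence does not say each anesthesiologist uses one technique. It could mean that the operator chooses case by case, and the recruitment section could describe a role filled by several people. On those readings the two sections are not strict opposites and operators are not nested. This stands, and a reader who infers as fact that every operator is tied to one block goes beyond the text. It does not remove the problem. Case-by-case choice by an operator who knows the block brings confounding by preference or indication, and the unexplained pairing cannot be relied on to prevent it.

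A reader might also infer that no later analysis could ever separate technique from operator. That is exact for one operator per arm and for operator fixed effects. With several operators per arm, an operator-level or random-effects analysis can account for random operator variation. It relies on the two sets of operators being exchangeable, which nested data cannot verify and a non-randomised design does not support.

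A third inference is that only the delivery rule is at fault, so that dropping the assignment sentence would cure it. That sentence is the only statement of how a patient reaches a group, and the recruitment section does not say which patient gets which block. Even with both blocks in the same hands, separation needs operator recorded and modelled. A within-operator contrast also still compares a newer technique with one the operator may know better.

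Blinding of PACU staff is a genuine strength against assessment bias, but it does not act on operator differences. Finally, the error rates rest wholly on assumed inputs. They show what is possible and do not measure a defect.

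**Conclusion.** The concern holds in this form: the two sections conflict and must be reconciled, and under any of the available readings the plan lacks the variable and the analysis needed to keep operator differences out of the technique comparison. If the operator determines the block, systematic operator differences are inseparable from technique and covariate adjustment will not help. If operators use both blocks, separation is possible in principle but is not achieved by the tests planned.

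The illustrative false-positive rate of about 8% to 33% against a nominal 5% depends on the assumed SD, arm size, between-operator SD and number of operators, and on nesting. The document supplies none of these. It does not establish that operators are nested, nor that any particular bias will occur.

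**What to change.** 1. Reconcile the PROTOCOL and recruitment sections into one assignment rule that also states how each individual patient's block is determined. Which rule to adopt is for the investigators; the statistical need is that it be single and explicit.
2. Add operator code and hospital to VARIABLES EVALUATED, with operator experience in the technique if available.
3. In the STATISTICAL ANALYSIS PLAN, where operators deliver both blocks, make the technique comparison within operator, by stratification or a mixed model, and include ease of performance.
4. Where operators deliver only one block, state that the study compares packages of technique plus operator, and do not attribute differences to the block alone.

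The cost is one or two extra coded fields, possibly a third for experience, and some loss of precision. Operators who use a single technique will add little to the within-operator contrast. The change must also go back for ethics re-evaluation, as the ETHICAL-LEGAL ASPECTS section requires. Operator code should be captured as the blocks are done, since it may not be recoverable afterwards.

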### **• Study population and total number of subjects.**

All patients consecutively scheduled for arthroscopic unilateral rotator cuff repair of the shoulder, who meet the inclusion criteria will be recruited for the study.

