## BACKGROUND AND JUSTIFICATION OF THE PROJECT

Arthroscopic shoulder surgery is related to a high incidence of postoperative pain, being rated as intense by 45% of patients in the immediate postoperative period (1). The management of these patients can be complex due to the high incidence of preoperative pain and its variability during the postoperative period, which is higher in patients undergoing rotator cuff repair surgery (2).

It is crucial to ensure adequate postoperative pain control in this type of intervention, especially in the context of major outpatient surgery. Adequate postoperative pain control can have several benefits, such as reducing hospital stay (3), accelerating postoperative rehabilitation (4), and improving long-term outcomes (5).

The PROSPECT guideline for rotator cuff repair surgery recommends associating a regional analgesic technique with a multimodal pharmacological approach to pain. (6).

Traditionally, the interscalene block has been considered the gold-standard for analgesia in shoulder surgery; However, its possible serious complications limit its use. Currently, most anesthesiologists choose to perform more distal peripheral nerve blocks of the brachial plexus (upper trunk block, supraclavicular block, infraclavicular block at the costoclavicular level, axillary nerve block...) which, although highly effective, continue to cause impairment. prolonged motor activity and are not free of complications (phrenic paralysis, transient nerve injuries, inadvertent vascular punctures...) (7).

Shoulder anterior capsular block (SHAC) has recently been described. It is a fascial block of the anterior capsule of the shoulder that aims to avoid motor impairment while maintaining optimal analgesic efficacy (8)(9). However, so far only anatomical and descriptive studies of small case series have been published. Therefore, this research work, with the objective of comparing the postoperative analgesic effectiveness of two regional analgesic techniques: the SHAC block associated with the suprascapular nerve block performed anteriorly vs. suprascapular and axillary nerve blocks performed posteriorly in operated patients. of the shoulder via arthroscopic procedures that cause intense postoperative pain.

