## **MATERIAL AND METHODS**

### **1.1 Definition of study subjects**

The inclusion criteria: being over 18 years of age, ASA physical status I – III and having been scheduled for shoulder arthroscopy surgery.

The exclusion criteria: any contraindication for performing regional anesthetic techniques (infection at the puncture point, alteration of hemostasis, allergy to local anesthetics, patient refusal to participate in the study, inability to evaluate postoperative pain, known neuropathy of the operated limb and patients who required conversion to open surgery).

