## **STATISTICAL ANALYSIS PLAN**

Continuous quantitative variables will be expressed as mean and standard deviation and the results will be contrasted using the Student's T test if normality criteria will be met, failing which they will be expressed as median and range and contrasted using the Mann Whitney's U. The qualitative variables will be expressed in absolute numbers and relative frequencies and the results of both groups will be contrasted using the Chi square. In addition, Fisher's test will be applied when necessary. Normality tests will be conducted for all continuous quantitative variables. The Kruskal-Wallis technique will be also employed with post-hoc application of the Bonferroni test for the analyses. The data will be processed using SPSS software version 19.0 (IBM Corporation, Armonk, NY, USA), assuming a p-value below 0.05 as significant.

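### Non-randomized groups are compared only with unadjusted tests, and the preoperative NRS that is collected is not used to adjust the postoperative pain comparison

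*Combined protocol and SAP*

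**What the plan says.** **Allocation.** The STUDY TYPE section describes "An observational study of paired cohorts, not randomized", in two hospitals. The PROTOCOL section states that "patients will be assigned to one of the study groups depending on the anesthesiologist responsible for performing the blocks". The recruitment section reads differently: the responsible anesthesiologist carries out both techniques "until the number of patients established in each of the groups is reached". Neither account is random. No section names a pairing factor or a matching method.

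**Outcome.** In VARIABLES EVALUATED, the definition begins "The main variable will be the measurement of pain intensity according to the NRS at different times: preoperative" and continues with hours 1, 2, 12 and 24 after surgery. The preoperative value is thus part of the main variable.

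**Analysis.** For continuous variables the STATISTICAL ANALYSIS PLAN says that "the results will be contrasted using the Student's T test if normality criteria will be met", and otherwise Mann-Whitney is used. Qualitative variables get chi-square or Fisher. Kruskal-Wallis with Bonferroni is also named. There is no regression, ANCOVA, stratification, matching, propensity method or paired test.

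**Prognosis.** The background describes a "high incidence of preoperative pain and its variability during the postoperative period, which is higher in patients undergoing rotator cuff repair surgery".

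**Population.** The abstract recruits "All patients consecutively scheduled for arthroscopic unilateral rotator cuff repair of the shoulder". Section 1.1 asks only for "having been scheduled for shoulder arthroscopy surgery".

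**The concern.** The stated purpose is to compare the analgesic effectiveness of two techniques. Without randomization, nothing in the design makes the groups alike before the block. If the patients of one anesthesiologist, list or hospital arrive with more pain, part of that difference carries through to postoperative NRS. An unadjusted test then assigns it to the block. The protocol itself flags preoperative pain as relevant and collects it, but the plan does not use it for the one purpose that a non-randomized comparison most needs. Bonferroni deals with multiplicity and does not help here.

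At stake are the size of the reported block difference and the meaning of p < 0.05.

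**Working it through.** The plan states no sample size, effect or SD, so there is no figure of its own to reproduce. What follows shows how large the effect could be.

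**From the documents:** significance level 0.05 (two-sided assumed); NRS 0 to 10; t test if normality holds, otherwise Mann-Whitney.

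**Assumed:** no true block effect; 50 or 100 patients per group; SD 2 for preoperative and postoperative NRS; slope 0.4 of postoperative on preoperative NRS; a systematic preoperative difference d of 0.5 or 1 point.

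**Closed form.** Bias b = slope × d. Standard error SE = SD × √(2/n). False-positive rate = Φ(−1.96 + b/SE) + Φ(−1.96 − b/SE).

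| n per group | d | b | SE | b/SE | False-positive rate |
|---|---|---|---|---|---|
| 50 | 0.5 | 0.4 × 0.5 = 0.20 | 2√(2/50) = 0.400 | 0.50 | 0.072 + 0.007 = 8% |
| 50 | 1 | 0.4 × 1 = 0.40 | 0.400 | 1.00 | 0.169 + 0.002 = 17% |
| 100 | 0.5 | 0.20 | 2√(2/100) = 0.283 | 0.71 | 0.105 + 0.004 = 11% |
| 100 | 1 | 0.40 | 0.283 | 1.41 | 0.293 + 0.000 = 29% |

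**Simulation with the plan's own test rule.** NRS was rounded and cut to 0–10. The t test was used if Shapiro-Wilk gave p > 0.05 in both groups, otherwise Mann-Whitney. There were 1500 runs per scenario.

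| Preoperative difference | n = 50 | n = 100 |
|---|---|---|
| none | 5.5% | 4.3% |
| 0.5 point | 6.9% | 8.8% |
| 1 point | 14.7% | 25.8% |

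These rates lie a little below the closed form, as expected when the scale is rounded and bounded. Allowing for simulation error, I take about 7% to 10% for 0.5 point and about 15% to 26% for 1 point. With preoperative NRS in a regression, the rate returns to about 5%.

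**Other assumptions.** With slope 0.3 to 0.5, SD 2.0 to 2.5, 30 to 100 per group and d of 0.5 to 1, the bias is 0.3 × 0.5 = 0.15 to 0.5 × 1 = 0.50 point, and the rate is about 6% to 42%. At the unfavourable end (slope 0.5, SD 2, d = 1), the simulated t test rejects in 15.8%, 21.9% and 41.7% of runs at 30, 50 and 100 per group. ANCOVA rejects in 4.6%, 4.6% and 5.3%.

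**Two limits.** The return to 5% holds because preoperative NRS is the only confounder in these runs. The runs also ignore that PACU morphine is titrated to NRS < 3, so the NRS rates at 1 h and 2 h may be too high. Ward tramadol has no such target, so this caveat does not extend to 12 h and 24 h.

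**The case against.** **No imbalance is shown.** Nothing says that the anesthesiologist's identity tracks patients' pain. If it does not, the unadjusted tests keep about 5%. This stands, and it is why the point is about protection and not a demonstrated error.

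**Baseline pain is already compared.** Preoperative NRS belongs to the main variable, and continuous variables are contrasted between groups, so an imbalance would not be hidden. Under the assumptions above, that contrast is significant in 67% to 92% of runs for a 1-point imbalance, but in only 21% to 41% for 0.5 point. This stands in part: the reader would often be warned, but a baseline test does not correct the later estimate.

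**Stronger readings that a reader might infer.**
- *Preoperative opioid use is a confounder that the plan overlooks.* The documents never mention it. With 5% versus 15% users (doubled dose, 1 point more pain), the simulated rates are 5% to 7%, close to nominal. Its absence from VARIABLES EVALUATED does not show that it goes unrecorded: that section lists outcomes and also omits age, sex and weight, and the annex text is not available.
- *Procedure mix differs between groups.* This is possible only if section 1.1 (any shoulder arthroscopy) governs. Under the abstract, all patients have rotator cuff repair.
- *Several imbalances add up.* A 0.5-point pain difference, 70% versus 90% cuff repair and 5% versus 15% opioid users, all in one direction, give 21% to 36% for NRS. That needs three assumed imbalances to align.
- *Rescue morphine is as badly affected.* Under that same combination, the morphine rates are about 19% and 34% (50 and 100 per group) if every patient with NRS > 3 gets rescue. The PROTOCOL section also requires functional impact. If half of those patients qualify, the rates fall to about 10% and 15%.

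**Conclusion.** The point holds in limited form. Allocation is not random, the label of paired cohorts has no stated content, and the only tests planned are unadjusted ones for independent groups. A baseline measure that the protocol itself treats as relevant is collected but not used for adjustment, so an imbalance in it would bias the estimated block difference by about the slope times the imbalance: 0.2 to 0.4 NRS point for a 0.5- to 1-point difference at slope 0.4. The false-positive rates above are illustrations that depend on that slope, SD 2 and 50 to 100 per group; the documents supply none of these.

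Adjustment removes the bias from preoperative NRS only. Because the PROTOCOL section ties technique to anesthesiologist, operator differences remain the most direct confounder, and other unmeasured factors remain too. The documents do not support saying that the groups will differ, or that opioid use or procedure type will distort the result.

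**What to change.** In the STATISTICAL ANALYSIS PLAN:

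1. Make the leading between-group analysis of NRS at 1, 2, 12 and 24 hours a regression (ANCOVA) on group, adjusted for preoperative NRS, with robust standard errors. State that preoperative NRS is taken before the block. Adjust for hospital as well, unless technique coincides with it.
2. Keep the unadjusted tests and label them supportive, so that there is no choice between two sets of p-values after the results are seen.
3. Use the same covariates for PACU morphine and for 24-hour tramadol, analysed separately.
4. If section 1.1 governs, record procedure type (cuff repair or other) and adjust for it. Recording preoperative opioid use from the chart is optional.
5. Report these factors and the anesthesiologist by group. If operators perform both techniques, as the recruitment section suggests, include operator as a covariate or cluster. If each operator performs only one, operator and block cannot be separated, and the report should say so.
6. State the conclusion as an association.

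**Cost.** One regression per outcome and at most two chart fields; allocation and care do not change. The interval widens if technique largely follows hospital or operator. For hospital the standard error grows by 1/√(1 − φ²), where φ is the correlation between technique and hospital. With one technique making up 70% of one hospital's cases and 30% of the other's, φ = 0.4 and the factor is 1/√0.84 = 1.09. At 90% versus 10%, φ = 0.8 and the factor is 1/√0.36 = 1.67.
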